**Taking Care of Us© Protocol (IRB Approval 9/25/2020)****Boston College IRB Protocol Number: 21.074.01****Funded by the National Institute on Aging (R21AG068715)****ClinicalTrials.Gov Identifier: NCT04737759****V. Research Summary:****A. Introduction and Background:**

Heart failure is the number one reason older adults are hospitalized in the United States. The proposed pilot study will evaluate a novel patient-care partner intervention (Taking Care of Us) that promotes 1) shared appraisal (i.e. similarity between how patients and their spouse care partners appraise the patient's symptoms), 2) communication between the patient and their care partner about their heart failure and related concerns, 3) collaboration between the patient and their spouse care partner to manage the heart failure together and 4) confidence of the patient and their spouse care partner to manage the heart failure as a means to improve the outcomes of both the heart failure patient and their spouse care partner. Facilitating and promoting shared appraisal, communication, collaboration and confidence are hypothesized to improve the physical and emotional health of both the patient and the spouse care partner. Specific aims and hypotheses are:

Aim 1 (primary): To determine the preliminary efficacy of the *Taking Care of Us* intervention on dyadic health.

*Hypothesis: HF care dyads in the Taking Care of Us group will have better dyadic (i.e., better health (primary outcome), lower depressive symptoms and anxiety, better dyadic health and less healthcare utilization) and individual health (i.e., lower care-related strain and better HF-specific QOL) compared with HF dyads in the control group.*

Aim 2: To determine the preliminary efficacy of the *Taking Care of Us* intervention on dyadic appraisal & dyadic management.

*Hypothesis: HF dyads in the Taking Care of Us group will have more similar appraisal of patient symptoms (i.e., dyspnea, pain, fatigue), greater collaboration in HF management behaviors, greater shared activities and greater communication and dyadic confidence compared with HF dyads in the control group.*

Aim 3: To determine the feasibility and acceptability of the *Taking Care of Us* intervention.

*We will determine feasibility and acceptability of the program to inform future studies.*

2. Provide the scientific or scholarly reason for this study and background on the topic

Heart Failure is a Major Public Health Problem: HF is the fastest growing cardiovascular disorder in the U.S., and most common reason for both hospitalization and rehospitalization among older adults. There are more than 1 million hospital admissions and 3 million emergency visits for HF in the U.S. annually. HF patients experience severe symptom burden, significant functional limitations, and poor QOL, with only 50% surviving five years post-diagnosis. Although family care partners make substantial contributions to the management of HF, experience poor health and significant care strain, they are rarely the focus of HF interventions. Thus, there is great need for novel dyadic interventions (i.e., interventions that target patient and care partner simultaneously) to reduce the family burden of HF.

Most non-pharmacologic HF interventions involve patient education and behavioral counseling, with limited success. Potential reasons for lack of efficacy include individual-based interventions, a focus on adherence only, and failure to acknowledge relational aspects of illness. Similarly, 50% of the small number of HF interventions (e.g. educational) targeting care partners only did not improve outcomes. Family-based interventions are more successful than individual interventions in chronic illness. In HF, involving care partners increases patient adherence; but, the majority of family-based HF interventions are focused on education and

specific aspects of adherence with little-to-no attention to care partner outcomes, HF management more broadly, dyadic management or the dyadic relationship. Moreover, prior studies have been inconsistent in efficacy. Indeed, current clinical guidelines (e.g. American Heart Association) call for greater family participation in HF management. Importantly, there also are calls from NIH for family self-management programs. Hence, theoretically- and empirically-driven dyadic interventions that are tailored to go beyond education are vital to address factors that impede dyads from collaborative HF management and optimize the health of both members.

There is strong evidence of the interdependence of health within dyads across chronic illnesses. The life- and QOL-limiting context of HF, unpredictable nature of the illness, and continual need for symptoms to be managed place considerable demands on HF patients and their care partners resulting in poor physical and mental health for both. Although dyadic research in HF is an emerging area, early evidence has confirmed the interdependence between patient and care partner health. Indeed, meta-analytic evidence shows that care partner health is associated significantly with HF patient health and clinical outcomes. Thus, there is strong scientific rationale for a dyadic approach to HF intervention research to optimize the outcomes of both members of the HF dyad.

The theoretical framework for the proposed study is our new Theory of Dyadic Illness Management. A product of extensive empirical evidence, our Theory of Dyadic Illness Management focuses on the care dyad as an interdependent team, with the goal to optimize dyadic health. How dyads communicate and collaborate to appraise and manage conditions like HF has great bearing on the health of the dyad as well as the health of each member of the dyad. Greater *shared appraisal* of patient symptoms and greater *collaboration, communication and confidence* around management of HF are purported to lead to optimal health of both members of the dyad.

### **B. Specific Aims/Study Objectives:**

The proposed dyadic intervention will be one of the first to target the outcomes of both the HF patient and their spouse care partner simultaneously through a team-based intervention centered on shared appraisal, collaboration, communication and confidence to promote optimal dyadic health. The proposed study is, therefore, significant in addressing an important gap. Our study will determine the feasibility, acceptability and clinical meaningfulness of the *Taking Care of Us* program.

Aim 1 (primary): To determine the efficacy of the *Taking Care of Us* intervention on dyadic health.

*Hypothesis: HF care dyads in the Taking Care of Us group will have better dyadic (i.e., better health (primary outcome), lower depressive symptoms and anxiety, better dyadic health and less healthcare utilization) and individual health (i.e., lower care-related strain and better HF-specific QOL) compared with HF dyads in the control group.*

Aim 2: To determine the efficacy of the *Taking Care of Us* intervention on dyadic appraisal & dyadic management.

*Hypothesis: HF dyads in the Taking Care of Us group will have more similar appraisal of patient symptoms (i.e., dyspnea, pain, fatigue), greater collaboration in HF management behaviors and shared activities, and greater communication and dyadic confidence compared with HF dyads in the control group.*

Aim 3: To determine the feasibility and acceptability of the *Taking Care of Us* intervention.  
We will determine feasibility and acceptability of the program to inform future studies.

### **C. Materials, Methods and Analysis**

The proposed study is a two-group randomized controlled trial with separate assessments of patients and spouse care partners at 0, two months and five months. A community-based sample of patient-spouse care partner dyads will be recruited and randomly assigned by block (patient gender) to either the *Taking Care of Us* intervention or to an educational attention-control. All sessions will be delivered via Zoom (or phone) - there will be no in-person contact with participants throughout the study. *The term spouse refers to spouse or*

*unmarried partner.* All participants will be assessed three times baseline, two months and five months. We believe 7 biweekly sessions over two months, with the first follow-up interview taking place immediately at two months is realistic and appropriate. Our second follow-up will take place at five months to explore sustained effects. The attention-control group will receive three educational sessions over two months (at approximately 0-, 4- and 8 weeks). The sampling frame for the proposed research is community-dwelling adults with NYHA class II-III HF and their spouse/partner. The target sample is 72 couples with HF (36 couples per arm) with equal gender representation.

Eligible and consented dyads will be randomly assigned to one of two groups. Block randomization stratifying by patient gender will be done using an online research randomizer ([www.randomizer.org](http://www.randomizer.org)). We will stratify by patient gender to ensure equal distribution between the two conditions. Participants will be provided with separate e-mail-specific links to the patient and spouse web-based survey using our REDCap platform; baseline surveys will take approximately 45 minutes to complete. Participants will be instructed to complete the survey separately without discussing the questions with their spouse/anyone else (this procedure has been successfully used in all dyadic work by this team and is the standard procedure in couple research). Participants who do not want to or cannot complete the survey electronically will be offered the option to complete the survey with a trained interviewer (blinded with respect to treatment assignment) via Zoom, phone or to complete a mail survey. Patients and their spouses will be interviewed separately and privately as in our other dyadic research. For the few participants who request a mail survey, they will receive individual packets and consent forms and return the survey and signed consent form in the stamped, addressed envelope provided. These procedures are identical to those successfully used by this team in other couple studies.

All Taking Care of US© (TCU) and educational sessions will be conducted via Zoom (or phone). Relevant materials for the sessions will be mailed to dyads ahead of the first session. For dyads in the TCU group, the project coordinator will inform the interventionist to schedule the first session with the dyad. The interventionist will communicate the treatment assignment to the dyad. Following completion of the 7 sessions of TCU, the interventionist will inform the project coordinator, who will schedule the immediate post-treatment interviews. For the control group, the trained educator (not involved in data collection) will contact the dyad to communicate their assignment to the attention-control condition and schedule a time for their first education session. Two additional education sessions will be done at 4 and 8 weeks. Following completion of the final education session, the trained educator will inform the project coordinator, who will schedule the immediate post-treatment interviews (approximately two months).

Follow-up web-based surveys will be done using our REDCap platform at two months and five months and will take approximately 30 minutes to complete (alternative modes of completion will be offered when necessary, e.g., by Zoom, phone or mail). The project director will make follow-up contact with each participant to confirm ongoing willingness to participate and ensure no change in e-mail address and to confirm preferred mode of completion. Participants will then be sent a follow-up e-mail with a link to the survey. At no time will RAs involved in collecting any data be aware of a dyad's treatment condition.

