### **Research Population & Recruitment Methods:**

The sampling frame for the proposed research is community-dwelling adult women and men with HF and their spouse care partner.

Formal inclusion and exclusion criteria for patient participants are:

Inclusion criteria:

Willing and able to provide written informed consent

Age greater than or equal to 18 years

Diagnosis of HF

Current HF symptoms (i.e. NYHA Class II-III; AHA/ACC Stage C HF)

Reachable by telephone/email/texting

Access to device with camera (e.g., computer, tablet) to participate in Zoom sessions or phone

Have a co-residing spouse/unmarried partner willing to participate

Exclusion criteria:

Major and uncorrected hearing impairment

Significant cognitive impairment

Heart transplantation/mechanical circulatory support prior to enrollment

Concomitant terminal illness that would impede participation in a longitudinal study

Active psychosis or severe substance abuse that would impair the ability to complete the study

Inability to complete the requirements of the study, including enrolment in an additional intervention trial

Formal inclusion criteria for spouse care partner participants are:

Age greater than or equal to 18 years

Co-residing with the patient at the time of recruitment

Have lived with the patient for a minimum of one year similar to other couple studies

Be willing and able to provide written informed consent

*Inclusion Criteria Justification:* An approximately equal number of women and men with heart failure will be enrolled. No potential participant will be excluded based on gender, race or ethnicity.

With 72 couples (144 participants total), and allowing for a 17% missing data rate, i.e. 60 dyads), we have 80% power to detect a 6.6 point difference in dyadic PROMIS global health scores between intervention and control groups (score mean=50, SD=10), which is greater than a minimally clinically important difference (estimate of  $\frac{1}{2}$  SD (5) due to no additional estimates available). These preliminary data are required to determine the sample size needed for a larger trial.

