provide interested heart failure patients with information about the study and contact information for the Boston College research team. Those dyads who are interested in the study and contact the research team will be screened by study staff not directly involved with patient care. Study staff will speak with both members of the interested HF dyad and determine eligibility. If both members of the HF dyad are interested and eligible, the project coordinator will ask participants to carefully read and provide written informed consent using an online consent/HIPAA authorization form via our Research Electronic Data Capture (REDCap) platform. (In rare circumstances where participants cannot or do not want to complete this process electronically we will mail a consent form and stamped, addressed return envelope). Regardless of mode, we will describe the study in detail, make sure participants have all of their questions about the study addressed and obtain written informed consent from all participants. Heart failure patients are often older in age, so as in our past studies, the option for reading the consent form detailing the requirements of participation will be offered to both patients and their care partners. In fact, reading aloud the entire consent form to potential participants has become the standard default in our current research. A copy of the consent form will be provided/sent to each participant (both members of the heart failure dyad). Participants can ask questions regarding the study on an ongoing basis. Waiver of elements of informed consent or HIPAA authorization will not be sought. We will not use parental consent, assent procedures, or any other form of proxy consent in this study.

**Tools that will be used to recruit** Recruitment flyers distributed in the community and through social media.

**Research Incentives and Payments:** Dyads will also be compensated with a \$100 gift card for their participation.

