**Informed Consent Procedure:**

All team members will attend virtual training hosted by the study MPIs. The training will include didactic presentations, roleplaying, feedback and problem solving about performance as well as study procedures and potential issues that may arise during sessions. The program will include information specific to HF and the components of the intervention/education programs as well as training for the RAs. Ongoing training will include review of completed forms to provide feedback on standardized protocol. To ensure independence of observations, interviewer, interventionist and control group educator training will be conducted separately. MPIs will closely monitor the interventionist and control group educator throughout the study to ensure fidelity of implementation by holding bi-weekly meetings. Treatment fidelity will be maximized by developing a standardized intervention manual in the first phase of the study.

The project coordinator and study staff will screen and obtain verbal consent and then direct eligible and interested dyads to complete written informed consent using an online consent/HIPAA authorization form via our Research Electronic Data Capture (REDCap) platform. All study staff will undergo training by the MPIs of the study as well as completing all necessary human subject education training.

After the consent form has been read to the participants we will ask them to summarize their understanding of the study and their participation. Participants will be strongly encouraged to ask questions about procedures and questions at all stages of the process.

Study staff will speak with both members of the interested HF dyad and determine eligibility. If both members of the HF dyad are interested and eligible, they will be asked to provide verbal consent to participate in the study. Once verbal consent has taken place, the project coordinator will first ask participants to carefully read and provide written informed consent using an online consent/HIPAA authorization form via our Research Electronic Data Capture (REDCap) platform.

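### The role that enrols dyads also learns their arms, allocation is in gender-stratified blocks, and the plan does not say how the next assignment is kept from enrolling staff

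*Combined protocol and SAP*

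**What the plan says.** Section C (Materials, Methods and Analysis) describes the allocation twice. The design paragraph has dyads "randomly assigned by block (patient gender"). The procedures paragraph says "Block randomization stratifying by patient gender will be done using an online research randomizer" and names a public website as the source. On timing it says "Eligible and consented dyads will be randomly assigned to one of two groups".

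The staff roles are spread over three sections:

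- **Enrolment.** Under Informed Consent Procedure, "The project coordinator and study staff will screen and obtain verbal consent and then direct eligible and interested dyads to complete written informed consent". Under Research Population & Recruitment Methods, "the project coordinator will ask participants to carefully read and provide written informed consent". Both sections also have study staff, in general terms, speaking with the couple and settling eligibility.
- **Intervention assignments.** In section C, "For dyads in the TCU group, the project coordinator will inform the interventionist to schedule the first session with the dyad". The interventionist then tells the dyad, and reports to the coordinator when the seven sessions are done.
- **Control assignments.** The educator tells the dyad. Who tells the educator is not stated. After the last education session the educator reports to the coordinator, who schedules the follow-up interviews.
- **Blinding.** The statements in section C cover interviewers and the research assistants who collect data. They do not mention enrolling staff.

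The patient exclusions include "Inability to complete the requirements of the study, including enrolment in an additional intervention trial", as well as significant cognitive impairment, for which no instrument or cut-off is given.

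The documents do not state who generates or holds the sequence, the block size, what triggers release of an assignment, or how the next one is hidden.

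**The concern.** Blocked allocation returns to balance at the end of each block, so anyone who knows the earlier assignments in a stratum can guess the next one better than by chance. Here one role takes part in screening and consent and, under the stated workflow, also learns assignments. If that person expects the next arm, a discretionary exclusion or a short delay is enough to influence which dyad receives it.

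The arms ask different things of couples: seven sessions against three. Couples who seem motivated could therefore be entered, even without intent, when the intervention is expected. That would bear on the Aim 1 comparison. It would bear more directly on the Aim 3 attendance, completion and retention figures, which have no baseline to adjust for. The protocol says these data will set the sample size of a larger trial, so a distortion would carry forward. Covariate adjustment cannot remove selection on motivation that was not measured.

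**Working it through.** **The plan's own figure.** The documents give no figure for predictability. The only design figure is 80% power for a 6.6-point difference with SD 10 and 60 analysable dyads (30 per arm). A normal approximation gives 0.82 with a one-sided 5% test and 0.72 with a two-sided one. With 36 per arm, two-sided, it gives 0.80. Alpha and sidedness are not stated. The present point does not depend on this; 6.6 serves only as a yardstick.

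**Inputs.** 72 dyads, 36 per arm, with equal gender representation, hence about 72/2 = 36 per gender stratum (section C). Recruitment is about 6 dyads a month, or roughly 3 per stratum. Block size is not given. I take 2, 4 and 6 as assumptions, and also one block of about 36 per stratum, because the design paragraph can be read as making gender itself the block.

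**Step 1: how often the next arm is guessed.** The best guess is the arm with fewer assignments so far in the stratum. For a block of 2m the expected number of correct guesses is m + (4^m / C(2m, m) − 1)/2, and dividing by 2m gives the rate p. For blocks of 4: 2 + (16/6 − 1)/2 = 2.833, and 2.833/4 = 70.8%. This rule needs the past allocations but not the block size.

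**Step 2: how often the next arm is certain.** If the block size is known too, the share of assignments fixed in advance is 1/(m + 1).

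**Step 3: difference between arms at entry.** Suppose entered dyads differ in prognosis by η points according to the guessed arm. The expected difference between arms is η(2p − 1). No document gives η. I take 2 points as an assumption and show 1 and 5 as a range; 5 is the plan's own half-SD threshold.

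| Block size | Correct guesses, p | Certain (of 72) | η = 1 | η = 2 | η = 5 |
|---|---|---|---|---|---|
| 2 | 75.0% | 50.0% (36) | 0.5 | 1.0 | 2.5 |
| 4 | 70.8% | 33.3% (24) | 0.4 | 0.8 | 2.1 |
| 6 | 68.3% | 25.0% (18) | 0.4 | 0.7 | 1.8 |
| 36 (one per stratum) | 59.1% | 5.3% (about 4) | 0.2 | 0.4 | 0.9 |
| Concealed | 50% | 0 | 0 | 0 | 0 |

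An exact recursion over the block gives the same guess rates and certain shares. The point differences assume that the enroller acts on every guess, so each is an upper figure for its η.

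**Step 4: what reaches the analysis.** The planned test is of GROUP on the slope, with baseline as a separate intercept. A difference in level at entry does not pass straight into that coefficient. It biases the test to the extent that selection relates to the rate of change.

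**The case against.** The strongest reply is that this is silence, not a described fault. A reader might infer that the coordinator holds or can read the list, which would make every assignment foreseeable and pass the full assumed 2 points to the comparison. No section says so, and drawing a sequence from a website does not make it an open list.

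A reader might also infer that one person alone judges eligibility and knows every earlier assignment at once. The text does not go that far. Study staff share the screening. The relay of assignments is explicit only for intervention dyads. For controls, the coordinator is expressly informed only after the last session, at about 8 weeks. Earlier knowledge follows by elimination in a two-arm trial, but that is an inference.

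Three more points have weight. Eligibility and consent come before assignment. Couples mostly refer themselves or are referred, at about 6 a month, which limits scope for choosing among them. And this is a pilot of preliminary efficacy.

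These points lower the likely size of any bias; they do not close the gap. Randomising after consent protects only if the next arm is unknown when eligibility is judged. At about 3 dyads per stratum a month, past assignments are easy to follow. Reports on controls reach the coordinator while recruitment, planned over 12 months, is still running.

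**Conclusion.** The point stands as a gap in allocation concealment that should be closed. It is more than a missing detail, because following the workflow as written lets someone who enrols track past assignments within gender-stratified blocks.

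Foresight would be 68% to 75% for blocks of 2 to 6, and about 59% if each stratum is a single block, against 50% with concealment. With η = 2 the arms would differ at entry by about 0.4 to 1.0 points, against a 6.6-point target. These figures rest on known past allocations, an assumed block size, an assumed η and action on every guess. They show what the design permits, not that bias will occur.

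The documents do not support saying that the list is open, that the coordinator alone decides entry, or that an entry difference becomes an equal bias in the treatment effect.

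**What to change.** - Load a gender-stratified list with randomly varying, undisclosed block sizes into the randomisation function of the REDCap system already in use.
- Have an existing team member who does not screen or consent load and hold the list.
- Release each assignment only after eligibility and both members' consents are locked.
- State these arrangements in section C, and say there whether block means a permuted block or the gender stratum. If such a separation already exists in practice, writing it down is enough.
- Where practical, have someone who does not enrol handle arm-specific scheduling and completion notices.

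The last step matters more than it may seem. Varying, undisclosed sizes remove the assignments that would be certain, but guessing the arm with fewer assignments so far still works when the past is known. With blocks of 4 and 6 in equal numbers the rate is (2.833 + 4.1)/10 = 69%. For the same reason, rerouting only the release achieves little while completions are still reported to the coordinator. Only keeping past assignments from enrolling staff brings the rate towards 50%.

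The cost is a few hours of set-up, a wording change and slightly less exact balance within strata. If the notices are moved, some scheduling work shifts to another team member. Sample size, power and participant burden do not change.
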